#### Adverse reaction

An adverse reaction is defined as a response to a medicinal product which is noxious and unintended. Response in this context means that a causal relationship between a medicinal product and an adverse event is at least a reasonable possibility. Adverse reactions may arise from use of the product within or outside the terms of the marketing authorization or from occupational exposure. Conditions of use outside the marketing authorization include off-label use, overdose, misuse, abuse and medication errors.

#### Serious adverse event

A serious adverse event is defined as any AE which

- results in death,
- is life-threatening,
- requires in-patient hospitalization, or
- prolongation of existing hospitalization,
- results in persistent or significant disability or incapacity, or
- is a congenital anomaly/birth defect.

Life-threatening in this context refers to a reaction in which the patient was at risk of death at the time of the reaction; it does not refer to a reaction that hypothetically might have caused death if more severe.

Medical and scientific judgement should be exercised in deciding whether other situations should be considered serious reactions, such as important medical events that might not be immediately life threatening or result in death or hospitalization but might jeopardize the patient or might require intervention to prevent one of the other outcomes listed above. Examples of such events are intensive treatment in an emergency room or at home for allergic bronchospasm, blood dyscrasias or convulsions that do not result in hospitalization or development of dependency or abuse. Any suspected transmission via a medicinal product of an infectious agent is also considered a serious adverse reaction.

**Adverse Event of Special Interest (AESI)**

The term Adverse Event of Special Interest (AESI) relates to any specific AE that has been identified at the project level as being of particular concern for prospective safety monitoring and safety assessment within this study, e.g. the potential for AEs based on knowledge from other compounds in the same class.

No AESIs have been defined for this study.

**11.2 ADVERSE EVENT AND SERIOUS ADVERSE EVENT COLLECTION AND REPORTING**

The investigator shall maintain and keep detailed records of all AEs in their patient files.

**Collection of AEs**

The study design is of non-interventional and non-drug related nature. Sufficient data from controlled interventional trials are available to support the evidence on the safety and efficacy of the studied BI drug. For this reason the following AE collection and reporting requirements have been defined.

The following must be collected by the investigator in the (e)CRF from signing the informed consent onwards until the end of the study:

- all adverse drug reaction (ADRs) (serious and non-serious),
- all AEs with fatal outcome

All ADRs, including those persisting after study completion must be followed up until they are resolved, have been sufficiently characterized, or no further information can be obtained.

The investigator carefully assesses whether an AE constitutes an ADR using the information below.

**Causal relationship of adverse event**

The definition of an adverse reaction implies at least a reasonable possibility of a causal relationship between a suspected medicinal product and an adverse event. An adverse reaction, in contrast to an adverse event, is characterized by the fact that a causal relationship between a medicinal product and an occurrence is suspected.

Medical judgment should be used to determine the relationship, considering all relevant factors, including pattern of reaction, temporal relationship, de-challenge or re-challenge, confounding factors such as concomitant medication, concomitant diseases and relevant history.

Arguments that may suggest a **reasonable causal relationship** could be:

- The event is **consistent with the known pharmacology** of the drug.
- The event is known to be caused by or **attributed to the drug class**.
- A **plausible time to onset of the event** relative to the time of drug exposure.
- Evidence that the **event is reproducible** when the drug is re-introduced.
- **No medically sound alternative etiologies** that could explain the event (e.g. preexisting or concomitant diseases, or co-medications).

- The event is typically **drug-related and infrequent in the general population** not exposed to drugs (e.g. Stevens-Johnson syndrome).
- An indication of dose-response (i.e. greater effect size if the dose is increased, smaller effect size if dose is diminished).

Arguments that may suggest that there is **no reasonable possibility of a causal relationship** could be:

- No plausible time to onset of the event relative to the time of drug exposure is evident (e.g. pre-treatment cases, diagnosis of cancer or chronic disease within days / weeks of drug administration; an allergic reaction weeks after discontinuation of the drug concerned).
- Continuation of the event despite the withdrawal of the medication, taking into account the pharmacological properties of the compound (e.g. after 5 half-lives). Of note, this criterion may not be applicable to events whose time course is prolonged despite removing the original trigger.
- Additional arguments amongst those stated before, like alternative explanation (e.g. situations where other drugs or underlying diseases appear to provide a more likely explanation for the observed event than the drug concerned).
- Disappearance of the event even though the study drug treatment continues or remains unchanged.

#### Intensity of adverse event

The intensity of the AE should be judged based on the following:

Mild: Awareness of sign(s) or symptom(s) which is/are easily tolerated

Moderate: Enough discomfort to cause interference with usual activity

Severe: Incapacitating or causing inability to work or to perform usual activities

The intensity of adverse events should be classified and recorded according to the Common Terminology Criteria for Adverse Events (CTCAE) criteria in the (e)CRF.

#### Pregnancy:

In rare cases, pregnancy might occur in a study. Once a subject has been enrolled into the study, the investigator must report any drug exposure during pregnancy, which occurred in a female subject or in a partner to a male subject to the Sponsor by means of Part A of the Pregnancy Monitoring Form. The outcome of the pregnancy associated with the drug exposure during pregnancy must be followed up and reported by means of Part B of the Pregnancy Monitoring Form.

In the absence of a reportable AE, only the Pregnancy Monitoring Form must be completed, otherwise the NIS AE form is to be completed and forwarded as well within the respective timelines.

**Expedited Reporting of AEs and Drug Exposure During Pregnancy**

The following must be reported by the investigator on the NIS AE form from signing the informed consent onwards until the end of the study:

Type of Report	Timeline
All serious ADRs associated with a BI drug taken for the disease in scope of the study	immediately within 24 hours
All AEs with fatal outcome in patients exposed to a BI drug taken for the disease in scope of the study	immediately within 24 hours
All non-serious ADRs associated with a BI drug taken for the disease in scope of the study	7 calendar days
All pregnancy monitoring forms	7 calendar days

The same timelines apply if follow-up information becomes available for the respective events. In specific occasions the Investigator could inform the Sponsor upfront via telephone. This does not replace the requirement to complete and fax the NIS AE form.

**Information required**

For each reportable adverse event, the investigator should provide the information requested on the appropriate (e)CRF pages and the NIS AE form.

**Reporting of related Adverse Events associated with any other BI drug**

The investigator is encouraged to report all adverse events related to any BI drug taken for the disease in scope of the study other than the according to the local regulatory requirements for spontaneous AE reporting at the investigator's discretion by using the locally established routes and AE report forms. The term AE includes drug exposure during pregnancy, and, regardless of whether an AE occurred or not, any abuse, off-label use, misuse, medication error, occupational exposure, lack of effect, and unexpected benefit.

### **11.3 REPORTING TO HEALTH AUTHORITIES**

Adverse event reporting to regulatory agencies will be done by the MAH according to local and international regulatory requirements.

## **12. PLANS FOR DISSEMINATING AND COMMUNICATING STUDY RESULTS**

The rights of the investigator and of the sponsor with regard to publication of the results of this study are described in the investigator contract. As a general rule, no study results should be published prior to finalization of the Study Report.

## **ANNEX 1. LIST OF STAND-ALONE DOCUMENTS**

The stand-alone documents for this non-interventional study are:

- Patient Informed Consent Form
- Patient's Caregiver Informed Consent Form
- Statistical Analysis Plan (SAP)
- Data Management Plan (DMP)
- Monitoring Plan (MP)
- Serious Adverse Event Report in Non-Interventional Studies (NIS (S)AE Form)
- Pregnancy Monitoring Form
- Publication Plan

All of the above documents will be archived in the Trial Master File in its original master version.

## **ANNEX 2. ENCEPP CHECKLIST FOR STUDY PROTOCOLS**

Not applicable.

## **ANNEX 3. ADDITIONAL INFORMATION**

1. *Patient diary*
2. *SGRQ questionnaire*
3. *EQ-5D-5L questionnaire*
4. *Zarit Burden Interview questionnaire*
5. *Barthel questionnaire*

1.2. STUDY TITLE

Observational Analysis on the Socio-economic Impact of IPF in Spain.

1.5. TYPES OF SITES WHERE THE STUDY WILL TAKE PLACE

It is planned that data of approximately 200 patients from approximately 25 sites (secondary care sites – Pulmonology services where IPF is diagnosed and managed) in Spain will be collected.

1.6. ETHICS COMMITTEE THAT EVALUATES THE STUDY

The study was presented to the specific ECs of the participating hospitals. The CEIC of acted as reference EC.

1.7. PRIMARY OBJECTIVE

To compare the economic impact of Idiopathic Pulmonary Fibrosis (IPF) according to FVC % predicted level (FVC<50%, FVC 50-80%, FVC>80%), in adult patients through estimation of annual direct costs (primary and secondary care visits, outpatient visits, emergency visits -

primary care and hospital-, hospitalizations,...), and indirect costs (days off work and informal caregiver) associated with the disease during one year.

1.8. STUDY DESIGN

Non-interventional multicenter study based on newly collected data of IPF patients followed-up for one year in secondary care settings (Pulmonology Services). IPF patients will be enrolled in a consecutive manner over a period of 6 month.

1.9. DISEASE(S) OR CONDITION(S) BEING STUDIED

Idiopathic Pulmonary Fibrosis (IPF)

1.10. DETAILS OF THE MEDICINAL PRODUCTS BEING STUDIED

Not applicable

1.11. STUDY POPULATION AND TOTAL NUMBER OF SUBJECTS

It is planned that data of approximately 200 IPF patients in Spain will be collected.

1.12. STUDY CALENDAR

Start of data collection: 29 November 2017

Planned end of data collection: August-2019

Planned final study report: December-2019

2. DICTIONARY OF ABBREVIATIONS

A description of the meaning of the abbreviations used in this document can be found below:

ADR	Adverse Drug Reaction
AE	Adverse Event
AESI	Adverse Event of Special Interest
BI	Boehringer Ingelheim
BMI	Body Mass Index
CA	Competent Authority
CCDS	Company Core Data Sheet
CI	Confidence Interval
CML	Local Clinical Monitor
CRA	Clinical Research Associate
CRF	Case Report Form
CTCAE	Common Terminology Criteria for Adverse Events
CTP	Clinical Trial Protocol
DLCO	Diffusing capacity of the lung for carbon monoxide
eCRF	Electronic Case Report Form
EQ-5D-5L	EuroQoL five dimensions questionnaire 5L
ENCePP	European Network of Centres for Pharmacoepidemiology and Pharmacovigilance
FDA	Food and Drug Administration
FVC	Forced Vital Capacity
GCP	Good Clinical Practice
GEP	Good Epidemiological Practice
GPP	Good Pharmacoepidemiology Practice
GVP	Good Pharmacovigilance Practices
IB	Investigator's Brochure
IEC	Independent Ethics Committee
IPF	Idiopathic Pulmonary Fibrosis
IQR	Interval quartile range
IRB	Institutional Review Board
MAH	Marketing Authorisation Holder Activities
Max.	Maximum

MedDRA	Medical Dictionary for Regulatory Activities
Min.	Minimum
NHS	National Health Service
NIS	Non-Interventional Study
PASS	Post-Authorization Safety Study
QoL	Quality of Life
SAE	Serious Adverse Event
SAS	Statistical Analysis System
SD	Standard Deviation
SGRQ	St. George's Respiratory Questionnaire
UIP	Usual Interstitial Pneumonia
6MWD	6 Minutes Walk Distance test

3. STUDY OBJECTIVES

3.1. PRIMARY OBJECTIVE

To compare the economic impact of Idiopathic Pulmonary Fibrosis (IPF) according to forced vital capacity (FVC) % predicted level (FVC<50%, FVC 50-80%, FVC>80%), in adult patients through estimation of annual direct and indirect costs associated with the disease during one year.

3.2. SECONDARY OBJECTIVES

- To estimate the QoL of the patients with IPF according to FVC % predicted level, through SGRQ and EQ-5D-5L questionnaires and the Barthel Index.
- To explore the determinants of costs and QoL in patients with IPF according to FVC % predicted level.
- To characterize acute IPF exacerbations along one year (frequency and cost) according to FVC % predicted level at baseline.
- To describe the variation of costs and QoL with IPF progression (according to the FVC deterioration).
- To explore the impact of disease on the patient's caregiver through Zarit Burden Interview questionnaire at 6 and 12 month.

4. STUDY POPULATION

4.1. ELIGIBILITY CRITERIA

It is planned that data of approximately 200 patients from approximately 25 sites (secondary care sites – Pulmonology services where IPF is diagnosed and managed) in Spain will be collected. All Idiopathic Pulmonary Fibrosis patients who are diagnosed with IPF and attend to a routine visit during the inclusion period and fulfill inclusion/exclusion criteria and provide informed consent to participate will be included in the study.

Patients can be included if all of the following criteria are met:

4.1.1. Inclusion criteria

1. Female and male patients \geq 40 years of age.
2. Patients diagnosed with Idiopathic Pulmonary Fibrosis (IPF) according to last ATS/ERS/JRS/ALAT IPF guideline for diagnosis and management consensus.
3. Written informed consent prior to participation.

4.1.2. Exclusion criteria

1. Inability for the patient to understand or complete the written Inform Consent or patients questionnaires or to understand Spanish.
2. Current participation in any clinical trial.
3. Patients for whom further follow-up is not possible at the enrolling site.

4.2. SAMPLE SIZE JUSTIFICATION

In view of the lack of Spanish studies that analyse the economic impact of IPF according to deterioration in the predicted FVC, and as this is a prospective observational study, it was decided to observe all the patients with IPF that meet the inclusion/exclusion criteria during the inclusion period. Based on the investigation into the viability of recruitment, we expect to include approximately 200 patients.

The primary objective of the study is to compare the economic impact of IPF according to FVC levels. This would mean opting for a balanced sample size for the three comparison groups.

However, knowing the approximate patient prevalence according to predicted FVC (5-11% predicted FVC $<50\%$, 51-73% predicted FVC 50-80%, and 22-38% predicted FVC $>80\%$) and the sponsor's internal data, we have estimated to find:

- 10-22 patients with predicted FVC $<50\%$.
- 102-143 patients with predicted FVC 50-80%.
- 43-76 patients with predicted FVC $>80\%$.

Depending on the final distribution obtained in terms of number of patients for each comparison group and given the exploratory nature of this study, it is expected that comparisons between some groups will have a descriptive approach, although the expected comparison analyses will be carried out as stated in this protocol (explorative statistical model if sample size allows). Although the expected number of patients with predicted FVC $<50\%$ is

small, it should at least provide first insights into the costs within this patient subgroup. In view of the lack of previous data on the cost of the disease according to the study's primary endpoint in Spain, this will be the first Spanish cost comparison study according to predicted FVC.

5. METHODS

5.1. DATA PROCESSING

A data management plan (DMP) was created to describe all functions, processes, and specifications for data collection, cleaning and validation (version v2.0_20180711).

5.2. DATA ANALYSIS AND STATISTICAL TESTS

5.2.1. Protocol deviations

The next table defined the different categories of protocol violations (PVs). The final columns describes which PVs were used to exclude subjects from the different patient analysis sets, in case any of them would be detected during the study.

Description	Requirements	Patients excluded due to PV in Evaluable population	Patients excluded due to PV in Safety population
IC1. Patients under 40 years of age or with no specified age	not met as specified in the protocol	All	None
IC2. Patients without diagnosed with Idiopathic Pulmonary Fibrosis (IPF) according to last ATS/ERS/JRS/ALAT IPF guideline for diagnosis and management consensus	not met as specified in the protocol	All	None
IC3. No written informed consent prior to participation	not met as specified in the protocol	All	All
EC1. Inability for the patient to understand or complete the written Inform Consent or patients questionnaires or to understand Spanish	met as specified in the protocol	All	None
EC2. Current participation in any clinical trial	met as specified in the protocol	All	None
EC3. Patients for whom further follow-up is not possible at the enrolling site	met as specified in the protocol	All	None

5.2.2. Populations for analysis

Evaluable population: The analyses will be performed on a sample of assessable patients, which will include all patients who meet the selection criteria (no protocol deviations) and with predicted FVC classified.

Likewise, given the main objective of the study, patients for whom there is data on resource use due to IPF (primary care/secondary care/emergency visits, transport, hospitalization, outpatient tests, pharmacological and non-pharmacological treatment, caregivers [formal and informal], orthoprosthetic material, structural changes, economic aid, social services, lost work productivity, resource use due to acute exacerbations) will be considered valid for the main analysis.

Safety population: All patients screening with informed consent prior to participation.

5.2.3. Univariate descriptive analysis

Main sociodemographic and clinical variables will be collected in order to describe population included in the study.

Continuous variables will be described using means, standard deviations (SD) and 95% confidence intervals (IC), and medians and 25-75 percentiles. Categorical variables will be described using absolute and relative frequencies.

5.2.4. Analysis of the primary variable

To compare the economic impact of IPF according to predicted FVC% (FVC<50%, FVC 50-80%, FVC>80%), in adult patients through the estimation of annual direct and indirect costs associated with the disease)

Annual direct and indirect IPF-related costs will be quantified for each patient over the follow-up period of 12 months from the societal perspective and National Health Service (NHS).

Direct and indirect costs will be quantified according to resource use and days of sick leave.

5.2.5. Direct cost

Direct costs are costs related to the health care system and are divided into health and non-healthcare costs. By definition, **direct health costs** include hospital costs, outpatient costs, tests costs, treatment costs, etc., while **direct non-health costs** include transport costs, social services costs, essential adaptations of the patient's home costs, etc. Therefore, this study will be considered:

- **Direct health costs:**

- Number of primary care visits due to IPF (T6, T12, acute exacerbations)
- Number of secondary care visits due to IPF (pneumologist, nurse, nutritionist, psychiatrist, psychologist, respiratory rehabilitation, pneumologist home visit, nursing home visit, smoking consult cessation, other health professional) (T6, T12, acute exacerbations)
- Number of emergency visits (primary care and hospital) due to IPF (T6, T12, acute exacerbations)
- Number of hospitalizations due to IPF (time in emergency room, number of days in plant, number of days in ICU) (T6, T12, acute exacerbations)
- Number of outpatient tests due to IPF (T6, T12, acute exacerbations):
 - Laboratory test (hemogram, biochemistry, coagulation profile, erythrocyte sedimentation rate, liver profile, angiotensin converting enzyme, rheumatoid factor, antinuclear antibodies, another tests).
 - Pulmonary function test (spirometry, pulmonary plethysmography, carbon monoxide diffusion capacity, 6-minute walk test, another test).
 - Other examinations (x-Ray, high resolution computed tomography, bronchoscopy, bronchoalveolar lavage, transbronchial biopsy, lung cryobiopsy, surgical lung biopsy, arterial blood gases, another test).
- Non-pharmacological treatment due to IPF (liquid oxygen therapy, electric portable oxygen therapy, oxygen therapy concentrator, oxygen, oxygen therapy portable device, high flow nasal cannulas, non-invasive mechanical ventilation) (T6, T12, acute exacerbations).
- Pharmacological treatments due to IPF (except treatments administered in hospitalization) (T6, T12, acute exacerbations).

- **Direct non-health costs:**

- Transport (number of trips and km of displacement in taxi, number of trips and km of displacement in ambulance) (T6, T12, acute exacerbations).
- Formal caregiver (time dedicated to patient care with IPF) (T6, T12, acute exacerbations).

- Orthopaedic material (manual wheelchair, electric wheelchair, anti-bedsore cushion, orthopaedic bed, orthopaedic chair, other) (T12, acute exacerbations).
- Economic aid and formal social services (T12, acute exacerbations)
- Structural adaptations (change in the structure of housing, elevators on the stairs in common areas, complementary technical aids, vehicle adaptation, other) (T12, acute exacerbations).

Calculation of direct health costs

Visits: The cost of visits will be calculated by multiplying the number of visits (emergency, medical) by the corresponding unit cost, which will depend on the health care area (primary or secondary) in which the visit occurred.

Hospitalizations: To calculate the cost of hospitalizations, days of stay in each unit (ICU, ward) will be multiplied by the unit cost corresponding to each unit. The sum of the costs of each service will then be calculated. In addition, emergency room admission will be added: if length of emergency stay was “less than 24 hours”, emergency room visit cost will be considered; if length of emergency stay was “more than 24 hours”, one day of emergency stay cost will be considered. Data on intubation during hospitalization (yes/no) will be used as qualitative information and not calculated as a cost.

Outpatient tests and non-pharmacological treatment: The cost of outpatient tests and non-pharmacological treatment will be obtained by multiplying the natural units of resource use (number of tests) by the unit cost of each outpatient test.

Pharmacological treatment: The costs of pharmacological treatment will be calculated taking into account:

- **Pharmacological doses**

The total dose prescribed of each active ingredient during the last 6 months will be calculated by multiplying the dose prescribed by the time on treatment. The time on treatment will be determined according to the start and end date of treatment. The scheduled dose may be daily, twice a day, three times a day, alternate days, weekly, every 2 weeks, monthly or on demand. If the schedule dose is ‘*on demand*’ an average dose according to the technical data sheet will be calculated.

The calculations described above will provide the total dose that each patient has received for the observational period.

- **Costs**

For treatments dispensed in the pharmacy office, the unit costs for each treatment were calculated taking into account the retail price (RRP) plus value added tax (VAT). From the National Health System (NHS) perspective, the co-payment of the Spanish Royal Decree-Law 16/2012 will be applying:

- Reduced contribution medication: 10% of the retail price for medication belonging to ATC groups qualifying for reduced contribution, with a maximum contribution expressed in euros. For reduced contribution medicines with a maximum of €4.26 per package.
- Normal contribution medicines: copayment in this medicines group should be applied according to each individual situation and on declared annual income:

Medicines Co-payment	
Annual resident tax declaration	Patient's copayment
Income \geq 100.000 €	60%
Income 18.000-100.000 €	50%
Income $<$ 18.000 €	40%
Pensioners	10%
Civil servant	30%

The cost of each pharmacological treatment will be obtained by multiplying the total dose (taking into account the prescribed dose and the administration schedule) each patient has received for the observational period by the unit cost of each treatment. If the commercial brand and presentation are available, the unit costs will be those that correspond to the said commercial brand and presentation. If this information is not available, an average cost will be calculated taking into account all commercialized presentations.

The annual direct health cost will be calculated as the sum of the costs of medical visits, emergency room visits, hospital admissions, outpatient tests, non-pharmacological treatments, and pharmacological treatments.

Calculation of direct non-health costs

Transport: The cost of ambulances will be obtained by multiplying the number of trips made per unit cost. For journeys by taxi, the kilometres recorded for each journey will be multiplied by the total cost of journeys made during the observation period, and the result will be multiplied by the corresponding unit cost.

Paid caregivers: The cost of paid caregivers will be calculated by multiplying the number of hours per day of care given by the number of days. The result will be the number of hours of paid care during the observational period, and will be multiplied by the corresponding unit cost.

Orthoprosthetic material: The cost of technical aids will be calculated by multiplying the number of days the patient has required the aid by the daily cost, calculated according to the catalogues of orthoprosthetic benefits of the autonomous communities.

Financial aid and social services: The cost registered in the eCRF will be considered. The monthly cost will be multiplied by the time aid was received. If the monthly amount is 'unknown', the mean cost of patients with full data will be used.

Structural changes: The cost registered in the eCRF will be considered.

Direct non-health costs will be calculated as the sum of transport costs, paid caregivers costs, orthoprosthetic material costs, financial aid and social services costs, and structural changes costs.

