## **9.2.3 Study visits**

The visit flow chart list all data collected and indicates with an “x”, the visit when they are collected. All data collected must be supported in the patient’s source documentation.

Visit flow chart and data collection parameters:

	T0 Baseline Visit	T6 6 month visit (+/- 2 month)	T12 12 month visit (+/- 1 month)
Patient Informed Consent	x		
Patient’s informal caregiver Informed Consent (if applicable)	x	x	x
Inclusion / Exclusion Criteria	x		
Date of Birth (Age)	x		
Gender	x		
Employment status (employment and net incomes)	x	x	x
Anthropometric variables (weight, height and BMI)	x	x	x
Date of IPF diagnosis	x		
FVC (ml, %)	x	x	x
FVC % predicted 	x	x	x
FVC rate change by year	x		x
DLCO (mmol/min/kPa)	x	x	x
DLCO % predicted	x	x	x
The Barthel index	x	x	x

Proprietary confidential information © 2017 Boehringer Ingelheim International GmbH or one or more of its affiliated companies

	T0 Baseline Visit	T6 6 month visit (+/- 2 month)	T12 12 month visit (+/- 1 month)
6MWD	x		x
Smoking status 	x	x	x
Environmental and occupational exposures 	x		
Drugs of abuse 	x		
Exposure to drugs associated with pulmonary fibrosis 	x		
Exposure to viral infection with potential association with IPF 	x		
Concomitant diseases related to IPF (lung transplantation included)	x	x	x
pharmacological and non-pharmacological treatments related to IPF	x	x	x
Patient diary review	x	x	x
IPF related resource use: primary and secondary care visits, outpatient visits, emergency visits (primary care and hospital), hospitalizations, ICU with and without intubation, outpatient tests and other examinations, use of transport, use of formal and informal caregiver,		x	x
IPF related resource use: orthopedic material, formal social services, economic aid and structural adaptations.			x
Days off work due to IPF		x	x
Sociodemographic variables for the caregiver (if applicable): age, gender, employment and relationship with the patient.	x		
Work productivity from informal patient's caregiver (if applicable)		x	x
QoL of the patients (SGRQ and EQ-5D-5L questionnaires)	x	x	x
QoL of the informal patient's caregiver (Zarit Burden Interview). If applicable.	x	x	x
Acute IPF exacerbations 	x	x	x
Safety: Adverse Drug Reactions (serious and non-serious), fatal AE, pregnancy	x	x	x

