5.2.8. Statistical methodology

A descriptive analysis will be performed of all the variables recorded for the study population. For the continuous variables, the mean, the SD, the 95% CI of the mean, the median, IQR (P25-P75), min. and max, and valid n will be calculated. Categorical variables will be presented as absolute and relative frequencies (percentages).

For bivariate analysis, continuous endpoints may be compared across subgroups of population using two-sample t-tests or ANOVA (if normality criteria are met), or the Mann–Whitney U test or Kruskal-Wallis test (if normality criteria are not met). The categorical endpoints will be analysed using the Chi-square or Fisher test, as appropriate. If apply, lineal correlations between continuous variables will be analysed (Pearson or Spearman correlations).

Multivariate exploratory analyses (e.g. generalized linear models) will be applied which include costs (Total annual IPF-related costs) and quality of life (SGRQ and EQ-5D-5L in baseline visit-T0) as dependent variables, and the explanatory variables will be discussed based on previous bivariate analyses and clinical relevance with $p<0.1$. Sample size and constraints imposed by the analysis models may prevent to include all variables of interest in this setting.

For all exploratory statistical tests, a significance level alpha of 0.05 will be assumed.

The data analysis will be performed by using the SAS statistical package, version 9.4 or later.

All costs will be estimated per patient per year, and will be specified with respect to the different FVC % predicted level (FVC<50%, FVC 50-80%, FVC>80%) and total sample.

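### The SAP costs drugs over the last 6 months, the cost period is 12 months, and nothing says where the look-back starts or how the T6 and T12 totals are joined

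*SAP*

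**What the plan says.** SAP 5.2.5, under pharmacological doses, sets the look-back: "The total dose prescribed of each active ingredient during the last 6 months will be calculated by multiplying the dose prescribed". The other factor in that product is treatment duration, for which the section adds: "The time on treatment will be determined according to the start and end date of treatment". It then describes the result differently: "The calculations described above will provide the total dose that each patient has received for the observational period". The cost step in the same section multiplies the dose that "each patient has received for the observational period by the unit cost of each treatment".

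Drug use is recorded on three occasions: "Pharmacological treatments due to IPF (except treatments administered in hospitalization) (T6, T12, acute exacerbations". Protocol 9.2.3 gives the visit windows as "6 month visit (+/- 2 month") and "12 month visit (+/- 1 month"). Protocol 9.1 takes whichever routine visit lies nearest to month 6 or month 12.

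SAP 5.2.4 sets the cost period at 12 months of follow-up. SAP 5.2.8 adds: "All costs will be estimated per patient per year". SAP 5.2.9 charges a full year when an ongoing treatment has no start date and the diagnosis precedes 2018.

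**The concern.** Three time bases sit side by side for one cost item: 6 months, the observational period, and a year. Among the calculation rules in SAP 5.2.5, only the drug rule carries a fixed look-back. Paid care, for example, is summed over the observational period.

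A 6-month look-back at each visit tiles the year only if the visits are exactly 6 months apart and T6 is at month 6. Visits follow routine care, so other dates are to be expected. Two programmers could both follow this SAP and obtain different drug costs.

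Drug cost is part of annual direct health cost and so of the primary outcome, under both the societal and the NHS perspective. Protocol 7 says the newer antifibrotic agents changed the total cost of the disease. The FVC<50% group is expected to hold only 10 to 22 patients, so a few miscounted patients could move its mean.

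**Working it through.** **Inputs**
- Look-back: 6 months (SAP 5.2.5).
- T6: 6 ± 2, so months 4 to 8. T12: 12 ± 1, so months 11 to 13 (Protocol 9.2.3).
- Cost period: 12 months (SAP 5.2.4).
- Assumption, not in the SAP: one look-back at T6 and one at T12, neither cut at T0 or at the previous visit, and the two summed.

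**Formulas**
- Windows: [T6−6, T6] and [T12−6, T12].
- Never costed between the windows: max(0, T12−6−T6).
- Costed twice: max(0, T6−(T12−6)).
- Before baseline: max(0, 6−T6).
- Early follow-up missed: max(0, T6−6).

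**The plan's own figure.** With visits at months 6 and 12 the windows are 0–6 and 6–12. The sum is 6+6 = 12 months with no gap or overlap, which agrees with the stated 12 months.

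**Other allowed visit dates (months)**

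| T6 | T12 | Windows | Gap | Twice | Pre-baseline | Early missed |
|---|---|---|---|---|---|---|
| 5 | 12 | −1 to 5; 6 to 12 | 1 | 0 | 1 | 0 |
| 7 | 12 | 1 to 7; 6 to 12 | 0 | 1 | 0 | 1 |
| 4 | 13 | −2 to 4; 7 to 13 | 3 | 0 | 2 | 0 |
| 8 | 11 | 2 to 8; 5 to 11 | 0 | 3 | 0 | 2 |

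The T6-to-T12 interval runs from 11−8 = 3 months to 13−4 = 9 months.

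**What this does to individual patients**
- Visits (8, 11), start at month 5, still treated at T12: 3 + 6 = 9 months charged, against 11−5 = 6 true (+50%).
- Visits (8, 11), stop at month 2: 0 charged of 2.
- Visits (4, 13), course in months 4 to 7: 0 charged of 3.
- Visits (4, 13), treated since before T0 and stopped at month 2: 2−(−2) = 4 charged, against 2.
- Over all allowed visit dates, measured against true time from T0 to T12, the error is −3 to +3 months for starters. For stoppers already treated before T0 it is −2 to +2 months.
- Treatment unchanged since well before T0: 6+6 = 12 months for every pair of dates, because gaps and overlaps are offset at the other end.

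**Other readings the wording allows**
- Look-back cut at T0: with T6=4, unchanged treatment gives 4+6 = 10 months.
- One look-back only, at T12: 6 of 12 months stay uncosted.
- Dated exposure from T0 to T6 and from T6 to T12: T6 + (T12−T6) = T12, so 11 to 13 months with no gap or overlap, still to be brought to 12.

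**The case against.** The strongest reply is that the two summed look-backs appear nowhere in the SAP. The look-back phrase occurs once and is not tied to a visit. The sentences after it use start and end dates and name the observational period. Read as a whole, the section leans towards dated exposure over follow-up, and a careful programmer could calculate that. This stands as far as it goes: the miscount is conditional, not certain. But reaching the right answer means setting aside the 6-month words, and an analysis plan should not require that.

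The (4, 13) and (8, 11) pairs are also extremes. If a patient is seen every 3 months (an assumption) and has visits at months 8 and 11, a month-5 visit would normally exist and lie closer to 6. The T6 visit would then be month 5, the windows −1 to 5 and 5 to 11, and the error one pre-baseline month. So the 3-month figures are upper bounds, and the documents give no distribution of visit dates.

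A reader might infer that drug cost is wrong for anyone who starts, stops or changes treatment. The documents do not support that. Visits at months 6 and 12 give no error, and with visits at (4, 13) a first start after month 7 is counted correctly. If starts are spread evenly over T0 to T12 (an assumption), 6/13 = 46% of starters are counted correctly at (4, 13) and 3/11 = 27% at (8, 11).

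**Conclusion.** The point holds as an internally inconsistent and unanchored time window for one component of the primary outcome. It should be corrected before costs are calculated. If a look-back is applied at each visit and the two are summed, up to 3 months can go uncosted, up to 3 months can be counted twice, and up to 2 pre-baseline months can enter. If it is applied once, half the year is lost. The affected patients are those whose treatment starts, stops or changes in the relevant months, plus those on unchanged treatment with an early T6 if the look-back is cut at T0.

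It would be tempting to add that the error differs between FVC groups and so biases the primary comparison. That is plausible but not shown. Groups are set by baseline FVC, the errors run in both directions, and nothing in the documents links visit dates or treatment changes to FVC group. The size in euros is also out of reach, because the documents give no drug prices, switching rates or visit dates.

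**What to change.** In SAP 5.2.5, replace the 6-month restriction with time on treatment between T0 and T12, taken from the recorded start and end dates. Count each day once across the T6, T12 and exacerbation records. State whether drug cost is cut or scaled to 12 months when T12 does not fall at month 12. Use the same window in SAP 5.2.4, in both the dose and cost steps of 5.2.5, and in the full-year rule of 5.2.9, which remains the provision for missing start dates.

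Limit the scaling to drug cost. A blanket scaling of every item to 365 days would distort one-off items such as structural adaptations, and would inflate costs for patients who die or withdraw early. Those cases need their own stated rule.

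The cost is a short wording change in three SAP sections and one programming rule. It needs no new data beyond the treatment dates that the SAP already relies on.
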